3.1.2 Primary Outcome Variable

Flow-mediated dilation (FMD) of the brachial artery following 5 minutes of forearm occlusion will be measured using our ultrasound machine (8L-RS 4.0-13.0 MHz probe, Vivid q, GE Healthcare, Mississauga, ON) and FMD data will be analyzed using FDA approved software available from Medical Imaging Applications (Coralville, IA, USA). FMD will be calculated as: (peak hyperemic diameter-baseline diameter)/baseline diameter x 100. Peak hyperemic brachial arterial velocity (and subsequently shear stress) will be determined using Doppler ultrasound, and used for normalization of FMD.

3.1.3 Secondary Outcome Variables

Arterial stiffness will be assessed using tonometry (Complior, Alam Medical, Saint Quentin Fallavier, France) and reported as PWV in m/s. Arterial stiffness will be determined using carotid – radial pulse wave velocity (PWV), and PWV will be calculated from measurements of pulse transit time and the distance traveled by the pulse between recording sites. Systemic inflammation and immune response will be assessed via antecubital venipuncture and analyzed at the University of Alberta. Based on prior research, important biomarkers have been identified as being involved in the inflammatory process of asthma, and are useful in identifying specific atopic phenotypes.¹⁶ The biomarkers being analyzed will include C-reactive protein (CRP), eosinophils, neutrophils, periostin, interleukin-17 (IL-17), YKL-40, and specific immunoglobulin E (IgE).

3.2 Subject Selection and Withdrawal

3.2.1 Inclusion Criteria

To be eligible for this study, the participants have to be between the ages of 18 and 55. Asthmatics will have to present at the ED with an apparent asthma exacerbation. Stable asthma controls may have confirmed or unconfirmed asthma. Healthy control participants must be free of asthma.

3.2.2 Exclusion Criteria

Participants who at the time of the study have known heart failure or unstable cardiac disease, lung diseases other than asthma, current infections, smoking history > 10 pack years, or known metabolic conditions will be excluded from this study.

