3.1 Study Design

3.1.1 General Design

This study is a cohort study utilizing a repeated measure design. Asthmatic patients will be tested at 3 different time points:

- At the emergency department
- 48 hours following discharge
- 14 days following discharge

Stable asthmatic and non-asthmatic controls will be tested at two time points:

- Day 1
- 48 hours following Day 1

Vascular parameters such as flow mediated dilation (FMD; endothelial function) and pulse wave velocity (PWV; arterial stiffness) will be evaluated at each time point to assess vascular function. Blood samples will be obtained for analysis of systemic inflammatory response and immune response at each time point.

Participants will also be given Fitbit activity monitors for 7 days of monitoring, perform a full pulmonary function test (PFT) and complete 3 questionnaires; Asthma Control Questionnaire (ACQ), Asthma Quality of Life Questionnaire (AQLQ), and EQ-5D.

(A) Cohort studies

Definition of study groups:

Individuals experiencing an asthma exacerbation will be identified at the University of Alberta Emergency Department (ED). They will be recruited based on asthma being the primary physician diagnosis in the ED, with asthma being confirmed at a follow up visit using spirometry.

Stable asthmatic controls will be recruited from the general populations, as well as two local pulmonary clinics: The Lung Health Clinic, Edmonton, AB; and the University Lung Clinic, Edmonton, AB. These participants will be recruited if they have indicated they have been diagnosed with asthma. Both confirmed and unconfirmed asthmatics will be eligible.

Healthy controls will be recruited from the general population. They will be age-, sex, and BMI matched to the exacerbation group.

Blinding and avoiding bias:

Due to the nature of the study, blinding will not be applicable.

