Endothelial function - The endothelial function of the brachial artery will be evaluated after 10 minutes of rest in the supine position using ultrasound imaging (8L-RS 4.0-13.0MHz probe, Vivid q, GE Healthcare, Mississauga, ON). Baseline diameter of the brachial artery will be established, whereby the blood flow of the forearm will be occluded distal to the measuring site for the duration of 5 minutes. Upon release of the occlusion, the blood velocity and the brachial diameter will be monitored for 3 minutes, and later analyzed (Medical Imaging Applications, LLC, Coralville, IA, USA; EchoPAC PC software, version 110.x.x, GE Healthcare, Horten, Norway). Microvascular function will be evaluated as the velocity time integral-envelope of the first heartbeat of reactive hyperemia (VTI; m/s) and the velocity during reactive hyperemia (VRH) calculated as $VTI \times 60/HR$.²³ Shear stress during reactive hyperemia (SSRH) will subsequently then be calculated as $SSRH = 8 \times \text{flow} / \text{diameter}$ and as cumulative SSRH until the time of peak FMD%.^{24,25} FMD corrected for SSRH will be considered the main outcome for endothelial function in this study, and VRH and SSRH as indicators of microvascular function. Follow up tests will be conducted after a 12 hour fasting period when possible. Where applicable, the subjects will be asked to withhold any long-acting asthma medication for a minimum on 48 hours prior to the test, and short-acting asthma medications for 12 hours prior to the test.

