Do you currently smoke ?  No Have you ever smoked ?  No  Yes How long ago did you quit ? How much did you smoke? <small>_____ Days _____ packs/day</small> <small>_____ Months _____ year smoking</small> <small>_____ Years _____ pack years</small> <small>(# of packs per day * # of years smoked = # pack years)</small>	
 Yes <small>_____ packs/day</small> <small>_____ years smoking</small> <small>(# of packs per day * # of years smoked = # pack years)</small>	
Triggers Do any of the following trigger your asthma ? (check all that apply)	
 Cats  House dust/mites  Outdoor Environment  Other animals  Indoor mold  Weather  Perfume  Household Chemicals  Work Environment  ASA/NSAIDS  Exercise  Pollution  Other:  Food/Food additives  Indoor/Outdoor <small>Indoor/Outdoor</small> <small>Indoor/Outdoor</small>	

Asthma Form																							
Collector Initiate		Study ID #																					

What asthma medication have you been prescribed/taken/missed in the past two weeks?
 
(Include medication that has been prescribed but not filled and medication missed/not taken)
																							

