Inhaled anticholinergic  Atrovent  Atrovent  Atrovent  Atrovent  Other _____	 Existing  New
Other  Montelukast  Montelukast  Montelukast  Montelukast  Other _____	 Existing  New

Other medication use (including vitamins, supplements, and non-prescription ~~ie, aspirin~~):

Vaccination within the past month? YES NO
 Type: _____ UNKNOWN

Menstrual status:
 Contraceptives: N/A YES NO
 Post-menopausal: N/A YES NO
 Type: _____
 If NO: Date of first day of your last period: _____

Source Documentation Version Date: June 27th 2018

Asthma Form
 Collector Initiate Study ID #

Medical history:		
Asthma:	YES	NO
Other lung disease:	YES	NO
Heart condition:	YES	NO
Current infections:	YES	NO
Other known conditions:	_____	

Exacerbation History:

Number of exacerbations requiring ED care in past 12 months: _____
 Date of most recent exacerbation: _____

Allergies: YES NO

If YES, please list all allergies:

Current Status Within past 12 hours

Alcohol:	YES	NO	Time: _____	Amount: _____
Smoking:	YES	NO	Time: _____	Amount: _____
Exercise:	YES	NO	Time: _____	Amount: _____
Coffee/Tea:	YES	NO	Time: _____	Amount: _____
Food:	YES	NO	Time: _____	Type: _____

Asthma Action Plan reviewed? YES NO

Additional notes/comments:

Data collection completed by: _____

Source Documentation Version Date: June 27th 2018

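### Current smokers with up to 10 pack-years can enter all three groups, but smoking is neither matched nor in the ED-versus-control analysis, so a smoking imbalance could pass as an exacerbation effect on FMD

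*Combined protocol and SAP*

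**What the plan says.** - **Eligibility.** Section 3.2.2 has one smoking rule, applied to everyone: "smoking history > 10 pack years, or known metabolic conditions will be excluded from this study". Section 3.2.1 sets age limits and asthma status and asks nothing about smoking. For healthy controls its only group-specific condition is "Healthy control participants must be free of asthma".
- **Balance between groups.** Section 3.1.1 says of healthy controls: "They will be age-, sex, and BMI matched to the exacerbation group". Of stable-asthma controls it says "These participants will be recruited if they have indicated they have been diagnosed with asthma", with no matching on any factor. Exacerbation patients come from one emergency department. Stable-asthma controls come from the general population and two lung clinics, and healthy controls from the general population.
- **Analysis.** Section 3.4.2 plans an unpaired t-test of the ED visit against the control group for FMD, inflammation and arterial stiffness, a repeated-measures ANOVA within the exacerbation group, and an ANCOVA that corrects FMD for shear rate. The only other covariate mentioned is waist circumference, which section 3.3 lists as a possibility.
- **Data.** The Appendix 5 sheet asks about current and past smoking and derives pack-years ("of packs per day * # of years smoked = # pack years"). Under "Current Status Within past 12 hours" it also asks whether, when and how much the person smoked. Section 4 states that history and current status are collected partly to learn about possible confounders.

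**The concern.** The comparison is not randomised, so only matching and adjustment protect it from differences between the people who reach an ED with asthma and those who volunteer as controls. The protocol treats smoking as important enough to cap and to record in detail, yet smoking is neither a matching factor nor a model term. A current one-pack-a-day smoker of nine years (9 pack-years) is eligible for any group.

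If current smoking is more common among ED patients and smokers have lower FMD, the t-test will show lower FMD at the ED visit even when the exacerbation does nothing. If smoking is less common among them, the error runs the other way. The planned correction for shear rate is not a correction for smoking status. FMD is the primary outcome, and the ED-versus-control contrast is the first analysis listed. The same gap affects PWV and CRP.

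Because the use of the smoking data is not stated in advance, the decision to adjust would be made after the results are visible, in a study without blinding.

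**Working it through.** **1. The plan's own figure.** Section 3.4.1 gives 36 per group for a 13% difference in VTI, without SD or power, so it cannot be confirmed. Solving backwards for a two-sided 5% test at 80% power, the detectable difference is (1.960 + 0.842) × √(2/36) = 0.66 SD. This implies a VTI coefficient of variation of 13/0.66 = 19.7%. The smoking point does not depend on this figure; it supplies only the group size of 36.

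**2. Assumed inputs (none is in the documents).**
- Gap in the share of current smokers, ED patients minus controls: 10, 20 or 30 percentage points.
- FMD deficit in current smokers: 1, 2 or 3 FMD points.
- SD of FMD: 3 points.
- Two-sided test. Section 3.4.2 gives 0.05 but not the number of sides.

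**3. Formulas.**
- Bias = prevalence gap × FMD deficit.
- Standard error = 3 × √(2/36) = 0.707.
- Noncentrality = bias / 0.707. The rejection rate is that of a two-sided 5% t-test on 70 degrees of freedom with no true exacerbation effect.

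**4. Results, 36 per group.**

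| Gap | Deficit | Bias (FMD points) | Bias / SE | Rejection rate |
|---|---|---|---|---|
| 10 | 1 | 0.1 | 0.14 | 5.2% |
| 10 | 3 | 0.3 | 0.42 | 7.0% |
| 20 | 2 | 0.4 | 0.57 | 8.6% |
| 30 | 1 | 0.3 | 0.42 | 7.0% |
| 30 | 2 | 0.6 | 0.85 | 13.3% |
| 30 | 3 | 0.9 | 1.27 | 24.1% |

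The 24% needs the largest gap and the largest deficit together. With only one of them at its extreme and the other at its lowest value, the rate is 7.0%.

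**5. A larger sample does not help.** At 44 per group the standard error is 3 × √(2/44) = 0.640, and the low, central and high cases become 5.3%, 9.5% and 28.5%. The bias stays the same while the standard error shrinks.

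**6. Cross-check in SD units.** With gaps of 10 to 30 points and an assumed smoking effect of 0.3 to 0.8 SD, the bias is 0.03 to 0.24 SD, at most 0.24/0.66 = 36% of the detectable difference in step 1. By the normal approximation the error rate is 5.2% to 17.5%, and 7.1% for 20 points and 0.5 SD.

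Steps 2 to 5 are on the raw FMD scale. Section 3.3 names shear-corrected FMD as the main outcome, and the documents do not allow the same calculation there.

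**The case against.** **Smoking is not ignored.** The plan excludes heavier smokers, records status, dose and recent use, and says that history is collected with confounding in mind. This stands. The gap is that no stated analysis uses the data, not that the data are absent.

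**The size is assumption throughout.** This also stands. A deficit of 3 points is a full SD on the assumed scale, in people capped at 10 pack-years, and the low case is indistinguishable from 5%. The range shows that the effect could be trivial or material; it does not estimate it.

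**Smoking is one of several unused variables.** The form also records alcohol, coffee or tea, exercise and ED drugs, and only shear rate is a firm covariate. That is fair, but smoking is the lifestyle exposure that the protocol itself restricts.

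**A stronger reading concerns the within-patient comparison.** A reader might infer that patients cannot smoke while in the ED but smoke freely before the follow-up tests, so that the follow-up FMD is lowered and the within-patient and between-group errors run in opposite directions. The documents do not support this. They do not give the time from arrival to FMD, and a patient may have smoked shortly before arriving. A stable smoking habit largely cancels when patients are compared with themselves. A change in recent smoking would not cancel, but its direction is unknown.

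**An abstinence rule may look like the natural remedy.** The pre-test conditions in section 3.3 cover food ("Follow up tests will be conducted after a 12 hour fasting period when possible") and asthma drugs ("the subjects will be asked to withhold any long-acting asthma medication"), not smoking. A rule applied at follow-up and control tests, but not at the unscheduled ED visit, would make smoking conditions differ by design and could itself lower ED values relative to every comparator. Smoking in the past 12 hours as a time-varying covariate does not fit the planned ANOVA either, and under such a rule it would be confounded with visit.

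**Conclusion.** The concern holds for the comparison of the ED visit with each control group. The text establishes that current smokers up to the cap are eligible everywhere, that smoking is not balanced by design, and that the stated test does not adjust for it. A smoking difference could therefore be mistaken for an exacerbation effect on FMD, and likewise on PWV and CRP, although no size was worked out for those two.

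The illustration in FMD points puts the error rate of the nominal 5% test at about 5% to 24%, with about 9% in the central case, entirely on assumed prevalence, effect and SD. The documents do not show that an imbalance will occur, nor that the repeated-measures result is biased in a known direction. The change is worth making because it is cheap and removes a choice that would otherwise be made after seeing the data.

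**What to change.** 1. In section 3.4.2, replace the unadjusted t-tests of the ED visit against each control group by a linear model (ANCOVA) with group and current smoking (yes/no, from Appendix 5), for FMD, PWV and CRP. For shear-corrected FMD, add current smoking to the ANCOVA already planned.
2. State one sensitivity analysis of the same comparisons restricted to current non-smokers.
3. Confirm that stable-asthma and healthy controls complete the same smoking items. The only sheet shown is headed Asthma Form. If healthy controls do not complete it, add the items for them; the covariate cannot be used without them.
4. Report smoking in the past 12 hours by group and visit as a description only.

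**Cost.** SAP wording and one degree of freedom per model. The non-smoker analysis will be smaller and less precise. No new data are needed if item 3 is confirmed; otherwise a few questions are added for controls. A yes/no term will not remove differences in the amount smoked.

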3.3 Study Procedures

Asthmatic patients will be tested at three different times:

- Day 1) ED visit
- Day 2) 48 hours post discharge
- Day 3) 14 days' post discharge

Day 1, participants will be recruited by the Emergency Medicine Research Group (EMeRG). They will receive standard emergency care for their asthma and once stabilized, informed consent will be obtained. A venous blood draw will be done prior to discharge. Once stabilized, the participant will be taken to a private area either within the ED department or [name]

lab in Clinical Sciences Building to ensure no interference with ED procedures. Applanation tonometry will be done to measure PWV, followed by FMD to determine endothelial function. **Day 2** the participant will return and the same assessments as Day 1 will be performed with the addition of spirometry according to standardized guidelines.¹⁸ Medication will not be withheld prior to this assessment. A Fitbit will be given along with instructions to wear the device for 7 days.

Day 3 will consist of the same measurements done in the ED for Day 1, with the addition of 2 quality of life questionnaires, the standardized Asthma Quality of Life Questionnaire (AQLQs) and the EQ-5D (5L), and the Asthma Control Questionnaire (ACQ), finishing with a full pulmonary function test including post-bronchodilator spirometry to evaluate for airway reversibility (i.e. asthma)¹⁹.

The participants are being tested 48 hours following the exacerbation to determine if systemic inflammation is further increased following an exacerbation, or if the exacerbation is when inflammation is at its peak. This will inform us on whether the exacerbation itself is the stimulus for increased systemic inflammation, or if it is a consequence of a stimulus in the days prior. The 14 day follow up was chosen based on the information that CRP is generally recovered to normal values after 14 days following stimulus,²⁰ as well, it is expected that lung function will have recovered 14 days following an exacerbation, as seen in other pulmonary disease exacerbations.²¹ Day 3 will tell us what average values for the participant would most likely be and allow us to compare the values obtained from the exacerbation against a personal reference value.

Stable asthmatics and healthy control participants will be tested at two different times:

- Day 1) date that participant is available for testing
- Day 2) 48 hours after Day 1

Controls are being tested at two times to determine the degree of natural fluctuations in endothelial function, arterial stiffness, and systemic inflammation in healthy adults.

Measurements

Waist Circumference – Using a fabric tape measure, waist circumference will be measured at the level of the last rib to the nearest 0.1 cm after a normal expiration.¹⁷ This will be used as a measure of adiposity and will potentially be used as a covariate during statistical analysis.

Arterial stiffness - Arterial stiffness will be evaluated using pulse wave velocity (PWV) between the carotid and femoral arteries. After 10 minutes of resting in a dark, quiet room in the supine position, cPWV and pPWV will be recorded using applanation tonometry (Complior, Alam Medical, Saint Quentin Fallavier, France). A series of 10 consecutive beats will be taken with a minimum quality of 85%. The distance between the carotid and femoral artery, as well as the carotid and radial artery will be recorded in mm. PWV will be measured prior to FMD and blood collection, and will be taken on all 3 days of assessments. PWV is expressed as m/s and is calculated as $PWV = L/\Delta t$, with L being the distance between the two points and Δt being the time it takes for the pulse to get from site 1 to site 2.²²

Endothelial function - The endothelial function of the brachial artery will be evaluated after 10 minutes of rest in the supine position using ultrasound imaging (8L-RS 4.0-13.0MHz probe, Vivid q, GE Healthcare, Mississauga, ON). Baseline diameter of the brachial artery will be established, whereby the blood flow of the forearm will be occluded distal to the measuring site for the duration of 5 minutes. Upon release of the occlusion, the blood velocity and the brachial diameter will be monitored for 3 minutes, and later analyzed (Medical Imaging Applications, LLC, Coralville, IA, USA; EchoPAC PC software, version 110.x.x, GE Healthcare, Horten, Norway). Microvascular function will be evaluated as the velocity time integral-envelope of the first heartbeat of reactive hyperemia (VTI; m/s) and the velocity during reactive hyperemia (VRH) calculated as $VTI \times 60/HR$.²³ Shear stress during reactive hyperemia (SSRH) will subsequently then be calculated as $SSRH = 8 \times \text{flow} / \text{diameter}$ and as cumulative SSRH until the time of peak FMD%.^{24,25} FMD corrected for SSRH will be considered the main outcome for endothelial function in this study, and VRH and SSRH as indicators of microvascular function. Follow up tests will be conducted after a 12 hour fasting period when possible. Where applicable, the subjects will be asked to withhold any long-acting asthma medication for a minimum on 48 hours prior to the test, and short-acting asthma medications for 12 hours prior to the test.

Systemic inflammation and immune response – Serum CRP, IgE, periostin, YKL-40 and whole blood eosinophils, neutrophils, and IL-17 will be analyzed from venous blood collected at each assessment day at the end of the visit via antecubital venipuncture by a certified phlebotomist following specified guidelines.²⁶ With the participant sitting in a relaxed position, the upper arm will be occluded to increase the accessibility of the blood vessels. Once a vein is chosen (based on proximity to the surface, size, position and absence of scar tissue and/or pulsation), a sterile 25-gauge needle will be inserted at a 30-degree angle or less to initiate blood draw. Blood will be collected in anti-coagulant-free polypropylene tubes pre labeled with the participant's identification number, date and time, and visit number. After two tubes are collected, the tourniquet will be removed followed by the needle and pressure will be applied to the venipuncture site and held until the bleeding stops. Once collected, the blood will be left to clot for a minimum of 30 minutes followed by centrifuging at 1000g for 10 minutes at 4 degrees Celsius. The serum will be separated into aliquots of 75 µg immediately after centrifuging and then stored at -80 degrees Celsius until analysis. Analysis of inflammatory and immune markers will be completed at the University of Alberta.

Physical activity - Physical activity will be evaluated by step count using a Fitbit activity monitor (Fitbit Inc., San Francisco, CA). Participants will be instructed to wear the monitor on their wrist for 7 days, beginning the morning after Day 2 testing. It will only be removed to shower/bathe and to sleep. Total steps in each 24-hour period will be averaged and used to determine activity levels during the first week of recovery. Low active will be defined as <7,500 steps/day. Somewhat active will be defined as 7,500-9,999 steps/day. Active will be defined as > 10,000 steps/day.²⁷

Pulmonary function – all participants will undergo a full pulmonary function test, according to established clinical guidelines.^{19,20} The expiratory volume in 1 second (FEV₁) responses to

4x100 mg Salbutamol will be evaluated, and an increase in FEV₁ of $\geq 12\%$ and 200 ml will be considered positive for significantly reversible airway constriction.²⁸

Questionnaires – The participant will be asked to complete the Asthma Control Questionnaire (ACQ) to assess asthma control. The ACQ is a validated, simple 7 item questionnaire that asks questions regarding symptoms and rescue inhaler use in the last week.²⁹ The minimally important difference for the ACQ is 0.5 with scores ranging from 0 (totally controlled) to 6(severely uncontrolled).³⁰ Next the participant will be asked to fill out the standardized Asthma Quality of Life Questionnaire, which is a validated, disease specific health-related quality of life assessment that encompasses both physical and emotional impacts of asthma.³¹ This questionnaire contains 32 items across 4 domains, with a minimally important difference of 0.5 with scores ranging from 1-7 with higher scores representing better quality of life.³² Lastly, the EQ-5D (5L) will be completed by the participant to assess their generic health status and all related aspects in their quality of life.³³ The EQ-5D (5L) is a validated and reliable questionnaire consisting 5 domains, along with a visual scale to measure the participants own judgement on current health status.³⁴ Together, these questionnaires will give us a representations of the individuals experience with asthma, along with the physical

